19.5. Safety Analyses

Safety will be evaluated using the Local Skin Response (Appendix E) which will specifically assess the following nine pre-defined safety endpoints: erythema, edema, whitening, petechiae, pinpoint bleeding, purpura, crusting, blistering, burn, as well as other to be graded on a 5-point ordinal score.

Safety will be evaluated in the Intent to Treat (ITT) population which includes all treated subjects. Safety results will be displayed separately for Groups A and Group B. Analyses will include a summary of the incidence, severity, and relatedness of all reported local skin responses, adverse device effects, and unanticipated adverse device effects. In addition, the percentage with no adverse device effects will also be reported as well as the percentage according to worst overall degree; a similar evaluation will be performed for the worst degree for those at least related to the study treatment. The percent reporting each ordinal score per safety endpoint will be presented separately for each stratum and combined.

20. Histological Analysis

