To reduce pain and discomfort during laser treatment, the Investigator may recommend use of a topical anesthetic product, such as EMLA or LMX-4 cream, which is applied to the intended treatment area for approximately 60 minutes prior to treatment. The Investigator may also recommend use of a local intradermal injection of anesthesia, such as lidocaine or similar medication. Nonmedicinal methods may also be offered such as simple ice packs, or devices that provide cold air, such as a Zimmer cooling device (Cryo 6, Zimmer Medizin Systems, Irvine, CA). Subjects may also elect to be treated without anesthesia.

Test Spots

Test spots may be performed prior to treatment to help the Investigator establish appropriate treatment parameters to achieve the desired clinical endpoint such as erythema or whitening. Test spot parameters will be guided by subject skin type, lesion type, color or location among other factors. The procedure for test spots involves delivering a laser pulse to the skin at or near the treatment area using a low energy, fluence or other setting, and then increasing the relevant parameters until the desired clinical endpoint is achieved. For the PicoWay® laser system the clinical endpoint is most commonly erythema or whitening of the skin.

Laser Treatment

Study laser treatments will be administered using treatment parameters recommended by the manufacturer and study Sponsor, Candela Corporation. The treatment location, wavelength, handpiece, pulse energy, number of passes, and number of pulses will be documented in the case report form.

Benign pigmented lesions including dyschromia will typically be treated with either the 532 nm or 1064 nm Resolve™ Fusion, or 730 nm handpiece.

Wrinkles including fine lines will typically be treated with the 1064 nm Resolve™ Fusion handpiece.

The investigator will determine the treatment specific parameters including wavelength, energy, fluence, spot size and repetition rate for each subject based on the type, color and location of the lesion among other factors. For darker skin types FST V and FST VI the 1064 nm wavelength is most commonly used.

Pain Assessment

Immediately after each treatment subjects will be asked to rate the amount of pain experienced during treatment using an 11-point Subject Pain Scale ranging from 0 (No Pain) to 10 (Extreme Pain). The Subject Pain Scale is provided in Appendix C.

Local Skin Response Assessment

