Local skin responses will be assessed and recorded following each laser treatment, normally within the first 30 minutes. The Local Skin Response Form is provided in Appendix E and includes the following most commonly observed skin responses which are both anticipated and in some instances desired clinical endpoints:

- Erythema
- Edema
- Whitening
- Petechiae
- Pinpoint Bleeding
- Purpura
- Crusting
- Blistering
- Burning

Safety Assessment

Local skin responses occurring from prior laser treatments that are deemed more serious due will be recorded as Adverse Device Effects (ADE) on the appropriate study case report form. Examples of anticipated ADE that can be observed following treatment with the PicoWay™ laser include:

- Hyperpigmentation
- Hypopigmentation
- Scarring
- Infection
- Herpes Simplex Activation

Although highly uncommon in conjunction with PicoWay® laser treatments, any Unanticipated Adverse Device Effects (UADE) will also be recorded on case report forms and reported to the Sponsor and IRB as required.

Post-Treatment Care Instruction

Subjects will receive instructions on post-treatment care of their treated areas. These may include the application of a petrolatum gel (such as Aquaphor® or Vaseline®); use of a topical corticosteroid (such as Cortizone®); avoiding sun exposure or use of tanning equipment; and use of a sunscreen with sun protection factor (SPF) 30 or greater for the duration of study.

Telephone Contacts

The Study Doctor or staff will make up to three (3) attempts to contact subjects by telephone 10 days after each treatment (+/- 7 Days) to assess healing response.

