10.3. Follow-Up Visits

Subjects will be scheduled for follow-up visits at 4 ± 1 weeks, 8 ± 2 weeks, and 12 ± 2 weeks after their final study treatment visit, or approximately 1, 2 and 3 months. Additional visits may be scheduled by the Investigator as needed.

Photography

Treatment areas will be photographed at all follow-up visits using the same camera settings used previously at Baseline and Treatment Visits.

Subject Satisfaction

Subjects will be asked to rate their level of satisfaction with the study treatments thus far at each follow-up visit using the Subject Satisfaction Scale provided in Appendix C.

Skin Biopsy (optional)

Subjects who have provided prior written consent may have one or more skin biopsy taken from the treated area at the discretion of the Investigator. Biopsy procedure details are provided in the Treatment Visit section above.

11. Schedule of Events

The Study Schedule of Events is provided in Table 1.

NOTE: The Screening and Baseline / Treatment #1 Visits may be combined in the same visit.

NOTE: Fewer than four (4) Treatment Visits may be required to reach maximum expected clinical results in some subjects. Treatments may therefore be stopped, and subject placed into the Follow-Up phase at the discretion of the Investigator.

Table 1: Study Visits and Schedule of Events

Activity	Screening	Baseline Tx 1	Tx 2	Tx 3	Tx 4	1 Month Follow- Up	2 Month Follow- Up	3 Month Follow- Up
	0 to -2 Weeks	Day 0	Week 6 ± 2 Weeks	Week 12 ± 2 Weeks	Week 18 ± 2 Weeks	Week 22 ± 2 Weeks	Week 26 ± 2 Weeks	Week 30 ± 4 Weeks
Informed Consent	X							
Medical History/Concomitant Medications	X							
Inclusion/Exclusion Criteria	X							
Treatment Site ID	X							
Pregnancy Test	X	X	X	X	X			
Skin Biopsy (Optional)		X	X	X	X	X	X	X
Telephone Contact*		X	X	X	X			
Photography		X	X	X	X	X	X	X
Laser Treatment		X	X	X	X			
Subject Pain Score		X	X	X	X			
Subject Satisfaction			X	X	X	X	X	X
Safety Assessment (LSR, ADE, UADE)		X	X	X	X	X	X	X
Concomitant Medications	X	X	X	X	X	X	X	X
Study Exit								X

*10 Days post-treatment (+/- 7 Days)

12. Study Compliance

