21.1. Potential Risks

The study treatments to be administered in this trial carry risks of local skin responses that are common, expected, and at times even desired with study treatments. The skin responses are typically only trace to moderate, and transient in nature, resolving within a few days after treatment.

Common local skin responses or side effects of treatment include erythema, edema, whitening, petechiae, pinpoint bleeding, purpura, crusting, blistering, and burning following the treatment.

Examples of less common but potentially more severe or lingering local skin responses associated with PicoWay™ laser treatment include hyperpigmentation, hypopigmentation, herpes virus activation, infection and scarring.

Allergic reactions to the topical or injectable anesthesia products are also possible.

There is also a risk of eye injury associated with the use of any laser device. This risk is very uncommon as it is easily prevented if proper safety eyewear is used as required.

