30.1. Appendix A: Pigment Clearance Score Pigment Score

Score	Clearance	Description
1	0% - 24%	Poor response
2	25 - 49%	Fair Response
3	50 - 74%	Good response
4	75 - 94%	Excellent response
5	$\geq 95\%$	Complete response

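### The five more serious or longer-lasting harms that the protocol names have no item of their own on the skin-response form and no row of their own in the safety table, so their capture may be uneven.

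*Combined protocol and SAP*

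**What the plan says.** Section 19.5 evaluates safety with the Local Skin Response form in Appendix E and lists "nine pre-defined safety endpoints: erythema, edema, whitening, petechiae, pinpoint bleeding, purpura, crusting, blistering, burn". The same sentence then adds an unnamed write-in category to those nine: "as well as other to be graded on a 5-point ordinal score". The section goes on to promise the percentage at each grade for each safety endpoint, by stratum and combined. Separately, it summarises the incidence, severity and relatedness of all local skin responses, ADEs and unanticipated effects, with the percentage of subjects free of ADEs and the worst degree.

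Section 10.2 describes the nine reactions as anticipated and sometimes wanted. Under Test Spots it says that "the clinical endpoint is most commonly erythema or whitening of the skin". On timing: "Local skin responses will be assessed and recorded following each laser treatment, normally within the first 30 minutes".

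The other list is in two places. Section 21.1 says that the less common but potentially more severe or lingering responses to "laser treatment include hyperpigmentation, hypopigmentation, herpes virus activation, infection and scarring". Section 10.2 gives the same five after the words "Examples of anticipated ADE that can be observed following treatment with the PicoWay™ laser include", and sends them to a case report form as ADEs.

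Table 1 (section 11) has a row headed "Safety Assessment (LSR, ADE, UADE", marked at Tx 1-4 and at all three follow-up visits. Section 22.2 collects these effects from consent to study exit.

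**The concern.** The itemised, graded part of the safety analysis covers reactions that are expected, and in two cases sought. The five harms most likely to matter in a judgement of the device's safety have no item or row of their own. Whether they are recorded depends on a clinician deciding that a finding qualifies.

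That decision has little to guide it. The sentence in 10.2 says that responses from earlier treatments judged more serious are to be recorded as ADEs, but it breaks off where the reason or criterion should follow. A faint hypopigmented patch at eight weeks could be written up at one site and passed over at another.

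At stake is how an empty or near-empty line for scarring or pigment change can be read. If every subject was asked and examined for it, zero is an observation. If not, zero may mean only that nobody opened a record.

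**Working it through.** The plan gives no safety sample size, harm rate or precision, so there is no figure of its own to reproduce. The check compares the lists and traces the recording routes.

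**1. Item count**

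| List | Source | Items |
|---|---|---|
| Pre-defined endpoints | 19.5, Appendix E | erythema, edema, whitening, petechiae, pinpoint bleeding, purpura, crusting, blistering, burn (9) |
| Usual treatment target | 10.2, Test Spots | erythema, whitening (2 of the 9) |
| More serious or lingering harms | 10.2, 21.1 | hyperpigmentation, hypopigmentation, scarring, infection, herpes activation (5) |

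Overlap of the third list with the first: 0 of 5.

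**2. Routes by which one of the five can reach the data**

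- *Appendix E.* Only the write-in Other slots (six in the text available to us). They carry the same grades as the named items but prompt for nothing in particular.
- *ADE record.* Scheduled at every treatment and follow-up visit (Table 1), collected from consent to exit with onset, severity, action, relationship and outcome (22.2), and rated with Tables 4 and 5. What triggers a record is the unfinished, judgement-based sentence in 10.2.
- *Follow-up procedures.* The synopsis and Table 1 schedule a safety assessment at follow-up, but section 10.3 describes only photography, satisfaction and biopsy, so it adds no instruction on what to look for.

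**3. What the tables will show**

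The per-endpoint table has nine named rows plus other, so none of the five has a row of its own. The ADE summary will include any that were recorded, but 19.5 does not ask for it by type of harm, and it specifies no confidence interval for any safety outcome.

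**4. Denominator**

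The synopsis counts ADEs against the total number of laser treatments. Up to four treatments are allowed. As an illustration with 30 subjects treated four times, one scar is 1/(30 × 4) = 1/120 = 0.8% per treatment and 1/30 = 3.3% per subject. For a lasting harm the per-subject figure is the one a reader needs.

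**5. What a zero row could tell the reader**

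With no case among n subjects, the upper limit of the exact two-sided 95% interval is 1 − 0.025^(1/n):

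- n = 160 (enrolment ceiling): 2.3%
- n = 34 (planned evaluable, Group B efficacy): 10.3%
- n = 30 (planned evaluable, Group A efficacy): 11.6%

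The safety population is all treated subjects, so 30 and 34 are illustrations and not planned safety numbers. The limits mean what they say only if each subject was checked for the harm.

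**6. What cannot be computed**

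The size of any missed fraction needs a true harm rate and a capture rate. The documents give neither, so no loss is estimated here.

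**The case against.** The strongest reply is that ADEs are already central to the plan. The synopsis makes their incidence, severity and relatedness the primary safety endpoint, section 17.2 includes them, and 19.5 summarises them. All five harms are named in 10.2 as anticipated ADEs, and assessment is scheduled at every treatment and follow-up visit. Appendix E has graded write-in slots. The ADE case report form is not reproduced and may list the five by name. The skin-response form is not confined to the first half hour either, since the synopsis and Table 1 repeat it at follow-up. All of this stands.

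It rules out two stronger readings that a reader might draw. The first is that scarring and pigment change are under-counted, or left wholly to unprompted reporting. With scheduled ADE assessment, an unseen ADE form and no rates in the documents, that cannot be asserted. The second is that hypopigmentation would count only as efficacy, because Appendix A grades per cent clearance up to "Complete response". Hypopigmentation is a named anticipated ADE. Sections 9.1 and 18 ask evaluators to rate improvement, and nothing says how they would score a site lightened below the surrounding skin. An altered responder analysis on that ground would rest on a guess.

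The incomplete sentence in 10.2 could also be a fault of the public copy. If the full text states a clear criterion, that part of the point weakens. The missing items and rows remain.

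**Conclusion.** The point holds as a weakness of ascertainment and presentation. None of the five named harms is among the nine pre-defined endpoints or has a named item on Appendix E, and two of the nine are usual treatment targets. Recording the five depends on write-in slots or on an ADE trigger that is judgement-based and, as printed, unfinished. Milder or lingering cases may be missed or handled differently between sites.

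No under-count is demonstrated, and its size cannot be estimated from the documents. The conclusion assumes that the ADE form does not already solicit the five harms by name at each visit. If it does, what remains is to complete the trigger sentence and add the rows to 19.5. This is an inexpensive improvement worth making. It does not show that the safety analysis fails.

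**What to change.** 1. Add hyperpigmentation, hypopigmentation, scarring, infection and herpes activation as named present/absent items, completed at Tx 2-4 and at all follow-up visits. Grade severity with the labels that Appendix E and Table 4 already share.
2. List the five in 19.5 as pre-defined safety endpoints. Report per-subject incidence with exact 95% confidence intervals, by group and combined, counting each subject once in the combined row. Keep the per-treatment figure beside it.
3. Complete the ADE sentence in 10.2 so that it states what makes a response recordable. The criterion is for the sponsor to set.
4. Keep reporting same-day erythema and whitening by grade, labelled as expected responses. Counting them only if they persist would remove severe same-day reactions from the report.

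The cost is five form items per visit, a few sentences and a few table rows. Reported harm rates may rise because the harms are now asked about, and the report should say so.

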20.1. Light Microscopy

Skin biopsies will be processed for routine hematoxylin and eosin (H&E) tissue staining to allow light microscopy analysis of laser-tissue effects such as acute skin and pigment changes, wound healing, or other morphologic changes.

20.2. Scanning Electron Microscopy

Skin biopsies may be processed for scanning electron microscopy (SEM) by a third-party laboratory to allow analysis of laser-tissue effects such as acute skin and pigment changes, wound healing response, or other morphologic changes.

21. Risks and Benefits

21.1. Potential Risks

The study treatments to be administered in this trial carry risks of local skin responses that are common, expected, and at times even desired with study treatments. The skin responses are typically only trace to moderate, and transient in nature, resolving within a few days after treatment.

Common local skin responses or side effects of treatment include erythema, edema, whitening, petechiae, pinpoint bleeding, purpura, crusting, blistering, and burning following the treatment.

Examples of less common but potentially more severe or lingering local skin responses associated with PicoWay™ laser treatment include hyperpigmentation, hypopigmentation, herpes virus activation, infection and scarring.

Allergic reactions to the topical or injectable anesthesia products are also possible.

There is also a risk of eye injury associated with the use of any laser device. This risk is very uncommon as it is easily prevented if proper safety eyewear is used as required.

21.2. Potential Benefits

Subjects may benefit from participation in this study by experiencing partial or complete clearance of their benign pigmented lesions including dyschromia, or their wrinkles including fine lines. However, there is no guarantee that subjects will experience any beneficial clinical result at all.

22. Adverse Device Effects

22.1. Definitions

The following occurrences will be documented and reported as required for compliance with applicable regulations including 21CFR 812 and ICH GCP EC(R2).

Adverse Device Effect

An adverse device effect (ADE) is an adverse event related to the use of an investigational medical device in a subject, whether it is expected or unexpected.

Unanticipated Adverse Device Effect

An unanticipated adverse device effect (UADE) is any serious adverse effect on health or safety, any life-threatening problem or death caused by, or associated with a device, if

that effect, problem, or death was not previously identified in nature, severity, or degree of incidence in the protocol; or any other unanticipated serious problem associated with a device that relates to the rights, safety, or welfare of subjects.

22.2. Reporting

Anticipated device effects (ADE) and unanticipated adverse device effects (UADE) are collected from the time of subject consent until the subject exits the study. A description of the adverse event or device effect, date of onset, severity, action taken, relationship to study treatment and outcome are documented in the case report form. All adverse events or adverse device effects are followed until resolution.

The Investigator will submit to Candela and to the reviewing IRB a report of any unanticipated adverse device effect (UADE) that might have led to a serious adverse event if suitable action had not been taken, intervention had not been made; or if circumstances had been less fortunate within 48 hours but in no event later than 10 working days after first learning of the effect.

The Sponsor, upon learning of any unanticipated adverse device effect, shall immediately conduct an evaluation and report the results to IRB within 10 working days.

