22.3. Rating

The Investigator will assess the severity and relationship of all adverse effects. The following definitions will be used for severity assessment:

For all ADE and UADE reported, the Investigator will assign independent ratings for Severity and Relatedness to laser treatment in accordance with the descriptions found in Table 4 and Table 5, respectively.

Table 4: Severity Rating System for ADE/UADE

Score	Severity	Definition
0	None	Normal
1	Trace	Very minimal reaction resolved within 24 hours. Does not require medical intervention. No effect on daily activities.
2	Mild	Noticeable reaction expected to resolve within 7 days. Does not require medical intervention. No effect on daily activities.
3	Moderate	Noticeable reaction lasting more than 2 weeks. Possibly requires some medical intervention. May interfere with some daily activities.
4	Severe	Significant skin reaction lasting more than 6 months, or deemed permanent by Investigator. Requires significant medical or surgical intervention. Debilitating and prevents normal everyday activities

Table 5: Relatedness Rating System for AE/UADE

Score	Relatedness to Treatment	Definition
0	Not Related	Clearly related to other factors and not to laser treatment
1	Possibly Related	A reasonable temporal sequence from the time of study treatment but could have been produced by other factors
2	Probably Related	A reasonable temporal sequence from the time of study treatment but cannot be reasonably explained by other factors.
3	Related	A reasonable temporal sequence from the time of or stopping the investigational product, or reappears on repeat exposure, or there is a positive reaction at the application site.
U	Unable to Determine	Insufficient information to make a rational determination.

23. Investigational Sites

Investigational sites will be identified by the Sponsor and pre-qualified for participation prior to site initiation or subject enrollment.

24. Compensation

Subjects will receive PicoWay™ laser treatments in this study at no cost. Subjects will also receive a one-time honorarium of \$100.00 upon completion of the scheduled 12-week follow-up visit. Subjects consenting to skin punch biopsies will receive \$250.00 for each biopsy taken.

25. Monitoring Plan

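### Adverse device effects are graded partly by duration, but the protocol requires no resolution date, defines Mild by a forecast, and does not say when the grade becomes final

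*Combined protocol and SAP*

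**What the plan says.** Section 22.2 lists what is recorded for each event: a description, then "date of onset, severity, action taken, relationship to study treatment and outcome are documented in the case report form". Events "are collected from the time of subject consent until the subject exits the study", and the same section adds: "All adverse events or adverse device effects are followed until resolution".

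Section 22.3 has the investigator rate severity by Table 4. The duration elements are:

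| Grade | Duration element | Basis |
|---|---|---|
| 1 Trace | "Very minimal reaction resolved within 24 hours" | observed |
| 2 Mild | "Noticeable reaction expected to resolve within 7 days" | expected |
| 3 Moderate | "Noticeable reaction lasting more than 2 weeks" | observed |
| 4 Severe | "Significant skin reaction lasting more than 6 months, or deemed permanent by Investigator" | observed, or judgement |

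Each of these grades also refers to medical intervention and to daily activities.

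Severity is named in the primary safety endpoint, both in the synopsis and in section 17.2. Section 19.5 reports "the percentage according to worst overall degree" and repeats that summary for treatment-related effects. Neither 22.3 nor 19.5 says when a grade is assigned, whether it is revised, or which grade is analysed if it changes.

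**The concern.** A severity scale that depends on duration needs two dates, and the protocol asks for one. It also needs a single basis, and Table 4 uses more than one. A grade of Mild can be entered on the first day because it needs only an expectation. A grade of Moderate cannot be supported by observed duration until two weeks have passed. If a forecast grade is left in place after the event has outlasted the forecast, the worst-degree table will place that subject too low, and the listed fields will not show it.

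The events most exposed are the slow ones. Section 10.2 names hyperpigmentation, hypopigmentation and scarring as anticipated adverse device effects, and section 21.1 describes effects of this kind as potentially longer-lasting. At stake is whether the severity part of the primary safety endpoint can be reproduced from the recorded data.

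**Working it through.** The plan states no figure on this point, so there is none to reproduce. The check sets the texts against each other and then against the visit calendar.

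**1. Do the listed fields give a duration?** Duration = resolution date − onset date. Section 22.2 names the onset date only. The listed outcome item might carry a date, but the protocol does not say so.

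**2. Do Mild and Moderate exclude each other?** Take a reaction expected on day 1 to clear within 7 days that in fact lasts 21 days.
- Mild: the expectation was held, so its duration wording is met.
- Moderate: 21 days > 14 days, so its duration wording is met.

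The other elements need not separate them. Mild requires no intervention and no effect on activities. Moderate words both as possibilities, so an event with neither also fits Moderate. Duration is then the only discriminator.

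**3. Is there a gap in the bands?** Yes. A reaction observed to last between 7 days and 2 weeks matches no observed-duration category. It can be Mild only through the forecast.

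**4. Do scheduled contacts fall at the cut-offs?** Section 10.2 has skin responses assessed normally within 30 minutes of treatment, then a telephone call at day 10 ± 7, that is, from day 10 − 7 = 3 to day 10 + 7 = 17. No contact is fixed at 24 hours, day 7 or day 14. For a reaction that began on the treatment day and is still present, the nominal day-10 call falls inside the unassigned interval: the 7-day forecast has failed and the 2-week criterion is not yet met.

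**5. Can the 6-month criterion be observed before exit?** Six months is 6 × 30.44 / 7 = 26.1 weeks. Table 1 puts exit at week 30 ± 4 (weeks 26 to 34) and Treatments 2 to 4 at weeks 6, 12 and 18, each ± 2. The documents also give a narrower window of ± 2 weeks for the final visit; the wider one is used here.

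| Treatment | Nominal weeks to exit | Range at window limits |
|---|---|---|
| 1 | 30 − 0 = 30 | 26 − 0 = 26 to 34 − 0 = 34 |
| 2 | 30 − 6 = 24 | 26 − 8 = 18 to 34 − 4 = 30 |
| 3 | 30 − 12 = 18 | 26 − 14 = 12 to 34 − 10 = 24 |
| 4 | 30 − 18 = 12 | 26 − 20 = 6 to 34 − 16 = 18 |

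On the nominal schedule only Treatment 1 exceeds 26.1 weeks. At the window limits Treatment 2 can, and Treatments 3 and 4 never do. Section 6 also allows fewer treatments. With three, the time from Treatment 1 to exit is nominally 2 × 6 + 12 = 24 weeks, and then no effect reaches six months before exit. Other cases would need the judgement of permanence or follow-up beyond exit.

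**The case against.** The strongest reply is that the gap is smaller than it looks.

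- **The form is not in the documents.** Section 22.2 is a prose list, and the outcome item, or the duty to follow events to resolution, could bring a date with it. This stands. A reader might infer that the case report form has no end date; the documents show only that the protocol does not require one.
- **Other records give partial checks.** Table 1 schedules a safety assessment and photographs at every treatment and follow-up visit, section 19.1 has all data source-verified before lock, section 25 provides monitoring, and the recorded action taken bears on the intervention element. This also stands, so it would be wrong to say that severity cannot be verified. But visits weeks apart and a call with a 14-day window only bracket an end date, and source verification cannot check a field that nobody was asked to record.
- **Nothing freezes the first grade.** Section 22.3 requires rating by Table 4, and an investigator may well regrade. Section 10.2 describes adverse device effects as responses from prior treatments judged more serious, so with visits 6 ± 2 weeks apart many will be graded with some duration already seen. If grades are entered at successive visits, a worst-degree summary would take the higher one. A reader might infer that severity will be understated. The documents do not show that: forecasts can err both ways (a reaction graded Mild may clear within a day), and no regrading rate is given. What remains is an asymmetry at the Mild/Moderate boundary: before day 14 only Mild has support from its duration wording, so unrevised errors there run mainly downward.
- **Section 21.1 itself warns that pigmentary effects may linger.** That gives an investigator reason not to forecast a one-week course. It reduces the risk but does not remove it.

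**Conclusion.** The point holds as a defect in the grading rule and in required data capture. Mild and Moderate overlap for a reaction that outlasts its forecast, the protocol does not require the date that would settle the matter, and no section says which grade is final. Severity in the primary safety endpoint and in the worst-degree summary may therefore be misclassified, with a risk of understatement. Only the duration component is uncheckable, and only from the listed fields.

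No percentage can be attached. The documents give no adverse device effect rate, no distribution of durations and no regrading practice. The subjects affected would be those whose worst effect was graded Mild on expectation, lasted more than 2 weeks and was not regraded; this could be none. Safety is summarised descriptively, with no hypothesis in 19.2, so no test, power figure or efficacy result is touched. The point is worth correcting because the remedy is cheap and an end date not collected at the site cannot be reliably rebuilt later.

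The conclusion assumes that section 22.2 lists the required items in full and that no unseen form instruction fixes when severity is finalised. If the form already has an end date and a regrading rule, what remains is to state them in the protocol and to reconcile Table 4.

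**What to change.** 1. In 22.2, and on the form if it is not already there, add to the recorded items: date of resolution, or ongoing at study exit.
2. In 22.3 and 19.5, state that the analysed grade is the one confirmed at resolution or study exit against the recorded duration, and keep the first-report grade for listing.
3. Put the Table 4 grades on one observed-duration basis and reconcile the bands together. Rewording Mild alone is not enough: it would leave reactions of 7 days to 2 weeks with no duration band. The same revision should reconcile the 6-month criterion with the length of follow-up and say how an effect still ongoing at exit is graded. Where the cut-offs should lie is for the sponsor to settle.

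Section 19.1 calls for the SAP to be final before study initiation, so the rule in item 2 can be set there. The cost is one extra form field and revised wording in Table 4, 22.3 and 19.5. Sites already have to follow events to resolution, so the date should be obtainable with little extra work. The downside for the sponsor is that reported severity may look slightly less favourable.
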